cardiopulmonary exercise testing. If the preliminary results of this randomized phase Il study demonstrate that oxygen or high flow rate affect dyspnea intensity, the next step will be to conduct a larger multi-institutional, randomized controlled trial that is adequately powered to compare HFOx with a control intervention, particularly in the home setting. This would be a logical extension of the proposed study because the use of HFOx has predominantly been limited to the hospital setting. The technology that allows this device to be used at home in an affordable manner is just now becoming available (i.e., Flowrest device). Once the efficacy of HFOx is confirmed, patients will have *much more* access to this therapeutic measure. The proposed study has the

Figure 3. Study Flow Chart.

potential to greatly improve patients' symptom burden, function, and quality of life.

C. RESEARCH DESIGN AND METHODS

C.1. Overall study design (Figure 3). This is a 2x2-factorial, double-blind, randomized, controlled trial of HFOx, HFAir, LFOx, and LFAir in non-hypoxemic cancer patients with dyspnea. We plan to enroll 50 patients in total. Enrolled patients will first complete a baseline structured exercise session with LFAir and return 3±2 days later to be randomly assigned to receive one of the four study interventions during the second structured exercise session. We will use a computer-generated sequence in permuted blocks for randomization, stratified by baseline dyspnea modified Borg Scale and work rate. Even with 2 different flow rates, patients and research staff will be blinded to the gas (i.e., oxygen v. air); thus, this will remain a double-blind study. On the basis of our experience conducting symptom control trials, we believe this study design is feasible and will not be an undue burden for patients. The rationale for the current study design is as follows:

- **Factorial design**—This will allow us to examine the oxygen and high flow effects separately while providing preliminary data about synergism between oxygen and flow.
- **Parallel design**—This design will minimize study burden and attrition compared with a crossover study that requires 5 exercise sessions. We will adjust for inter- individual differences by accounting for both baseline dyspnea score and maximal work rate.

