- 2. Average dyspnea Borg Scale ≥4 of 10 with severe exertion over the past week
- 3. Oxygen saturation >90% on ambient air at time of assessment
- 4. Able to communicate in English or Spanish
- 5. Karnofsky performance status ≥50%
- 6. Age ≥18 years
- 7. Seen at Supportive Care, cardiopulmonary center, thoracic radiation oncology or thoracic medical oncology

Exclusion Criteria

- 1. Resting dyspnea modified Borg Scale >7 of 10 atenrollment
- Severe obstructive lung disease (FEV1/FVC <70% post bronchodilator and forced expiratory volume in 1 second <30% predicted)
- 3. Delirium (i.e., Memorial delirium rating scale >13)
- 4. History of unstable angina or myocardial infarction in the last week
- 5. Acute pulmonary embolus or pulmonary infarction in the last week
- 6. Thrombosis of lower extremities in the last week
- 7. Acute myocarditis, pericarditis, or endocarditis in the last week
- 8. Symptomatic aortic stenosis or syncope in the last week
- 9. Suspected dissecting aneurysm
- 10. Severe untreated resting arterial hypertension (>200 mmHg systolic, >120 mmHg diastolic) at the time of enrollment
- 11. Uncontrolled arrhythmias causing symptoms or hemodynamic compromise in the last week
- 12. Uncontrolled heart failure in the last week
- 13. Pleural effusion requiring thoracentesis within 1 week of study enrollment or scheduled during the study period
- 14. Airway obstruction requiring stenting within 1 week of study enrollment or scheduled during the study period
- 15. Pneumonia requiring antibiotics at the time of study enrollment

C.3. Screening and recruitment. Patients attending our supportive care, thoracic oncology, cardiopulmonarv or outpatient clinics will be screened for this study. Α two-step consent process will be used. First, verbal consent will be obtained by the study staff before screening potential participants to determine their eligibility. Outpatients may be contacted by phone within 1 week prior to their scheduled clinic visit to inform them of the study so that they can make necessarv the arrangements to participate. Eligible patients will be formally enrolled in the study after they have signed the informed consent form indicating their willingness to participate the trial. in Once enrolled. the research staff will work with the patient to identify the 2 ideal study days. We will document the number of who patients are screened. approached. eligible, enrolled, and

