C.7. Exercise ergometry will be conducted by a trained PROSPR exercise physiologist in accordance with the 2003 American Thoracic Society and American College of Chest Physicians guidelines (2003). We chose to use cycle ergometry instead of other modalities (e.g., a 6-minute walk test) to induce exertional dyspnea because a stationary bicycle makes it easier for us to deliver oxygen, monitor the physiologic parameters and work rate, and minimize falls. On the first day, we will administer the baseline questionnaires, including demographics, medication history, performance status, Edmonton Symptom Assessment Scale, dyspnea survey, cancer dyspnea scale, and dyspnea modified Borg scale. We will also measure patients' height, weight, resting ECG, resting blood pressure, and resting heart rate.

Before the start of exercise, research staff will explain the exercise test sequence to the participants, including how to use the dyspnea modified Borg scale. The patient will be asked to pedal at a cadence of approximately 60 rpm during the test. The metabolic cart (Parvo True One, Sandy, UT) will be used to monitor cadence, measure work rate during the exercise test, and control resistance on the cycle ergometer. Patients will begin by pedaling with no resistance for 60 seconds, followed by a warm-up stage of 120 seconds, pedaling at 10 watts (W) of resistance for the first minute and 20 W for the second minute. Their blood pressure and heart rate will be recorded every 2 minutes. Oxygen saturation and electrocardiography results will be monitored every 2 minutes during the exercise sessions. The dyspnea modified Borg Scale will also recorded every minute. Patients will perform cycle ergometry tests at an increment of 10 W/min without oxygen until they experience volitional fatigue. During the 3-minute recovery stage at 10 W, their blood pressure, heart rate, and dyspnea modified Borg scale (rating of perceived dyspnea scale, RPD) will be recorded every minute.

After at least a 2-hour rest period, patients will perform a structured exercise session, with an initial warm up period of ≤ 3 minutes followed by constant work rate cycle ergometry at 80% of the peak work rate and using LFAir, until they experience volitional fatigue. The work rate during this test will be used for stratification.

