During the second session, 3±2 days later, patients will be asked to repeat the structured exercise with one of the four study interventions. The study assessments conducted on the first day will be repeated. We will use the constant work rate test for the comparison because it has been found to be more responsive for dyspnea than have incremental tests (Teunissen et al. 2007). A gas exchange analysis will not be conducted because the high flow and oxygen content can interfere with measurements of VO2 (ml/kg/min), VO2 (L), VCO2 (L), VE (L), PetO2 (mm Hg), and PetCO2 (mm Hg), making accurate assessments infeasible. After consulting with our pulmonary collaborator and exercise physiology team (PROSPR), we have decided to measure the work rate and use this as a factor for stratification.

Although we do not expect patients to experience desaturation during exercise based on our previous studies, if we find significant hypoxemia during testing with LFAir or HFAir (and even LFOx and HFOx) arms, patients will not be able to continue with this study and will be considered as dropouts. The termination point is defined by (1)

2014-0971 Rev. 9/17/18 Page 9 of 15

participant volitional fatigue, (2) abnormal hemodynamic responses to increasing workload, (3) inability to maintain bike cadence, (4) arrhythmias detected on the ECG including changes suggesting ischemia, (5) loss of any monitoring signals, or (6) hypoxemia [O2 saturation <88%] while exercising. Patients will be monitored throughout structured exercise testing, and will have access to urgent medical care if needed. Because this study is designed to induce dyspnea with exercise and some participants had to stop the exercise testing due to leg cramps before they became dyspneic, we will ask study participants not to continue with the rest of the study if their maximum level of dyspnea Borg scale intensity is less than 4/10 by the end of the first incremental test (in keeping with inclusion criteria #2). We will enroll a total of 50 patients who completed all 3 exercise tests and had dyspnea of at least 4/10 at the end of the first incremental test.

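### C.7 calls a patient who desaturates in the randomised session a dropout, and D.2 names no analysis set that would keep that patient in the oxygen comparison

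*Combined protocol and SAP*

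**What the plan says.** C.1 places randomisation at the return visit: patients "return 3±2 days later to be randomly assigned to receive one of the four study interventions". Before that, C.7 has every patient do two exercise tests on day 1, neither with oxygen. The first is incremental: "Patients will perform cycle ergometry tests at an increment of 10 W/min without oxygen until they experience volitional fatigue". The second is a constant-work-rate test at 80% of peak on LFAir.

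C.7 then sets the hypoxemia rule. It opens by saying that "we do not expect patients to experience desaturation during exercise based on our previous studies". The condition it sets next is this: "if we find significant hypoxemia during testing with LFAir or HFAir (and even LFOx and HFOx) arms". The stated consequence for anyone who meets that condition is that "patients will not be able to continue with this study and will be considered as dropouts". The next sentence defines the termination point of a test by six events. Volitional fatigue is the first and "hypoxemia [O2 saturation <88%] while exercising" is the sixth. The paragraph ends with the enrolment target: "We will enroll a total of 50 patients who completed all 3 exercise tests" and reached the required dyspnea level on the incremental test.

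D.1 justifies 10 patients per arm and a total of 50 after allowing for 20% attrition. D.2 makes the Borg score at isotime the primary outcome, with isotime fixed by the last measurements of the baseline constant-work-rate test. It provides multiple imputation only when more than 10% of patients have missing data, without naming the imputation variables, and it names no analysis set. Oxygen saturation is a secondary outcome (A.3) and is analysed with mixed models (D.2). Entry requires "Oxygen saturation >90% on ambient air at time of assessment" (Table 1).

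**The concern.** Before randomisation, removing patients who desaturate only narrows the population. After randomisation it can break the comparison, because the event depends on the gas: patients breathing oxygen are less likely to fall below 88% than similar patients breathing air. The parenthesis in C.7 treats hypoxemia on oxygen as the less likely case. If dropouts leave the analysis, the air and oxygen groups are no longer the groups that were randomised.

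Two results are exposed. The primary oxygen effect shifts if the removed patients would have had different isotime Borg scores from the rest. The saturation comparison is exposed more directly, because patients would be removed according to the value of the outcome itself. The trial exists to supply effect sizes for a larger trial (A.1, B.5), from about 20 evaluable patients per gas, so even a few selective losses deserve a rule.

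**Working it through.** **1. Does the rule act after randomisation?** Day 1 uses only a test without oxygen and a test on LFAir. HFAir, LFOx and HFOx first appear in the second session, after assignment. Since the rule names all four arms, it covers the randomised session as well as day 1.

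**2. What status does a desaturating patient have?** C.7 makes significant hypoxemia a dropout event, and makes saturation below 88% a test endpoint on a par with fatigue. It does not say how the two relate, and 88% is the only number it gives. A patient who falls below 88% after isotime already has an observed primary score, yet would carry the dropout label.

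**3. Plan's own figures.** Two-sided noncentral t, alpha 5%:
- Main effect of 1 SD, 20 v 20, standard error √(2/20) SD: power 0.869 with 38 df, 0.867 with 34 df (two covariates).
- Interaction of 2 SD, standard error √(4/10) SD: 0.867 with 34 df.
- Enrolment: 40/(1 − 0.20) = 50.

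These agree with D.1 (86%, 86%, 50). They take 50 as the number before attrition. If 50 must complete all three tests, as C.7 says, the same attrition implies 50/0.80 = 62.5, or 63 enrolled. The two sections therefore count different things.

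**4. Bias formula.** Let p be the share of randomised air patients removed, and d the amount (in SD) by which their isotime Borg scores exceed those of other air patients. If the others average m, all air patients average (1 − p)m + p(m + d) = m + pd. Removal leaves m, so the oxygen contrast moves by p × d. The documents give neither p nor d. For a true benefit of 1 SD with removal on air only:

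| p | d | Estimate (SD) | Power, 20 v 20, 34 df |
|---|---|---|---|
| 0 | any | 1.00 | 0.87 |
| 4% | 1 | 0.96 | 0.84 |
| 10% | 1 | 0.90 | 0.79 |
| 20% | 1 | 0.80 | 0.69 |
| 20% | 0 | 1.00 | 0.87 |
| 20% | −0.5 | 1.10 | 0.92 |

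Simulation (25 per gas, 3,000 runs) gave 0.91 and 0.80 at p = 10% and 20% with d = 1. Multiple imputation from gas and flow alone gave the same 0.91 and 0.80. If prone patients on oxygen are removed half as often, the estimate at p = 20% is 0.89. With no true effect, p = 20% and d = 1 give a spurious 0.20 SD against oxygen.

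**5. What p is plausible after day 1?** Assume a fraction q would desaturate on air on any given day, with bivariate normal nadir saturations correlated r between days. Only one of the two day-1 tests is counted as a screen. Then p = (q − P(both days))/(1 − q).
- q = 10%, r = 0.6: (0.10 − 0.0390)/0.90 = 6.8%, or 1.7 of 25 air patients.
- q = 10%, r = 0.9: (0.10 − 0.0689)/0.90 = 3.5%, or 0.9 of 25.
- q = 20%, r = 0.6 to 0.9: 12.6% to 6.3%, or 3.2 to 1.6 of 25.

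With d = 1, the bias is about 0.03-0.07 SD at q = 10% and 0.06-0.13 SD at q = 20%.

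**The case against.** The strongest reply is that this will hardly happen. The plan expects no desaturation, and any patient who falls below 88% in either day-1 air test never reaches randomisation. An LFAir patient in the second session is repeating a test already passed, so the resting entry threshold is not the relevant margin. This largely stands, and it is why the estimated bias is small. It does not close the gap: day-to-day variation leaves some patients who desaturate only in the second session, and the rule was written for that case.

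A second reply is that the plan nowhere says recorded data are discarded. That is correct. A reader might infer that the lowest air-arm saturations are deleted and that dropouts are replaced. Neither is stated: the mixed models in D.2 could use values up to the stop, and D.1 counts attrition within the 50. The difficulty is that C.7's completer count points the other way and nothing settles it.

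A reader might also infer that the rule biases the oxygen effect toward zero. That needs two conditions the documents do not supply: oxygen truly reduces dyspnea, and patients who desaturate are more breathless at isotime. With d = 0 there is no bias, with d negative the effect is inflated, and with no true effect oxygen looks harmful.

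Finally, keeping scores up to the stop does not by itself supply the primary outcome. A patient stopped before isotime has no isotime score, and substituting an earlier score could understate dyspnea. This stands, and the fix must deal with it.

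**Conclusion.** The plan permits, without clearly prescribing, an exclusion after randomisation on an event that the randomised gas can affect. The text of C.7 and the lack of an analysis set in D.2 establish this without any numerical assumption.

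The effect on the primary estimate is of unknown size and probably small: about 0.03-0.07 SD if 10% would desaturate on air, d = 1 SD and the between-day correlation is 0.6-0.9. All three are assumptions. Its direction is conditional, and a loss concentrated in the air arms is plausible but unquantified. The threat to the saturation outcome needs no assumption about Borg scores, only that the dropouts' data are left out. This is a gap worth closing because closing it is cheap; it does not undermine the trial as designed.

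**What to change.** Leave the clinical stopping rule unchanged and amend the analysis wording in C.7, D.1 and D.2:

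- Limit the dropout label for hypoxemia to the tests before randomisation. In the second session, record such a stop as a termination point.
- Define the primary and secondary analysis set as all randomised patients in their assigned arm.
- If the stop is at or after isotime, use the observed isotime Borg score.
- If the stop is before isotime, treat that score as missing. Impute it, whatever the percentage missing, from a model that includes the Borg and saturation values recorded up to the stop and the day-1 constant-work-rate scores. Add a sensitivity analysis that allows the missing scores to be systematically different (not at random).
- Keep every recorded saturation value in the mixed models.
- Report hypoxemia stops by arm.
- Reconcile the 50 completers in C.7 with the 50 before attrition in D.1, and state the number to be randomised.

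The needed measurements are already scheduled (Borg every minute, saturation every two minutes), so no new data collection is required. The cost is a short amendment, slightly more analysis work, and reliance on imputation for the few early stops.

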- **Baseline exercise sessions on day 1**—Patients will first complete an incremental exercise test to familiarize themselves with the cycle ergometer and to identify their maximal work rate. They will then complete a structured exercise session with cycle ergometry at a constant work rate of 80% peak with LFAir, which will inform us of their dyspnea response and isotime.
- Use of LFAir at baseline test—Neither LFAir nor LFOx has been found to improve dyspnea in non-hypoxemic patients. This will address the placebo effect with nasal cannula use.
- Inclusion of HFOx and HFAir arms—To our knowledge, HFOx has not been tested in non-hypoxemic cancer patients. No study has examined the therapeutic role of HFAir in any patient population.
- **Inclusion of LFOx arm**—Although LFOx was found to be ineffective compared with LFAir during the 6-minute walk test, its utility has not been tested with cycle ergometry in cancer patients.
- Stratification—To minimize the possibility that baseline dyspnea and exercise performance will affect the outcome, we will stratify patients by this baseline dyspnea modified Borg Scale score at rest (0-3/10 vs. 4-7/10; >7/10 will be excluded) and by their work rate during the first structured exercise session (≤50 W vs. >50 W). The objective of stratified randomization is to ensure a balance of the treatment groups with respect to the various combinations of predictive variables (i.e., the baseline Borg scale and work rate). This will ensure that a similar number of patients from each strata are randomly assigned to each treatment arm but will not require a similar number of patients in each strata. Thus, stratification should not affect the enrollment rate.

2014-0971 Rev. 9/17/18 Page 6 of 15

C.2. Eligibility criteria. The eligibility criteria are shown in Table 1. The rationale for including patients with obstructive and restrictive lung disease in this study is that the mechanisms of dyspnea relief (e.g., trigeminal nerve stimulation and decreased breathing effort; see Figure 1) are applicable to both types of pulmonary disorder. To ensure homogeneity in the study population and patient safety, we will exclude patients with severe obstructive airway disease (FEV1/FVC <70% post bronchodilator and forced expiratory volume in 1 second <30% predicted).

Table 1. Study Eligibility Criteria

Inclusion Criteria

- 1. Diagnosis of cancer, with evidence of primary or secondary lung involvement

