C.9. Exertional dyspnea clinical trials (Hui et al. 2014). Our department has an invested interest in developing novel therapeutics for exertional dyspnea in cancer patients. We have just completed a double-blind, randomized controlled trial to determine the effect of subcutaneous fentanyl on exertional dyspnea. After a baseline 6- minute walk test, patients were given fentanyl or a placebo and then asked to repeat the test. We enrolled 20 non-hypoxemic cancer patients in 5 months, with 100% completion. We also currently have 2 active double-blind, randomized controlled trials with fentanyl pectin nasal spray (expected to complete accrual by Feb 2015) and fentanyl buccal tablet. Because these opioid trials can only enroll patients who are opioid tolerant there should be many eligible patients for the proposed study.

C.10. Co-interventions. We will ask patients to use their usual inhaled medications on the day of the test as appropriate.

C.11. Training of research staff. An orientation will be held with all research staff involved in this study to introduce them to the study design and standardize the provision of each intervention. Particular attention will be paid to ensuring that research staff provide patients with proper instructions so they understand the study assessments. We will also have several mock-ups for practicing the study procedures.

C.12. Data Safety Monitoring Board (DSMB). The MD Anderson DSMB will be providing monitoring for patient safety and data quality assurance purposes.

D. STATISTICAL ANALYSIS

D.1. Sample size justification. Using 10 patients per arm (assuming 20% attrition, 50 total), we will have 86% power to detect a 1-standard deviation (SD) main effect and 86% power to detect a 2-SD interaction effect (assessed as the difference between the joint effect and an additive effect) with an alpha of 5%. These are large effects, but the main objective is to obtain preliminary estimates of effect sizes. We have expressed the treatment effects as multiples of the standard deviation because we do not have valid preliminary estimates of the within-group standard deviations on which to base these calculations.

D.2. Analysis plan. For the primary analysis, we will use a general linear model, with a Borg dyspnea score at isotime as the outcome variable and including the following

2014-0971 Rev. 4/20/2017 Page 12 of 15

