parameters as covariates: flow rate, oxygen, flow rate-oxygen interaction, work rate, and baseline dyspnea at rest, prior to the first exercise test. Isotime is defined as the time of the last set of measurements before completion of the baseline constant work rate test. Because of HFOx, VO2 max cannot be accurately measured. Instead, we will calculate the work rate (in watts), defined as the resistance of the flywheel x distance/revolution (m/revolution) x pedaling rate (revolution/min) x time(minute).

Because dyspnea is also repeatedly measured over time, secondary analyses will include a mixed-effects linear model on the longitudinal dyspnea scores, using the same 5 model parameters. For all analyses, we will use data graphs and residual analyses to verify assumptions, with data transformations as necessary. If more than 10% of patients are missing data, we will use multiple imputation in our analyses. Recognizing that dyspnea in cancer patients may have multiple etiologies, we will document its potential causes and perform subgroup analyses to determine whether a particular patient group benefits more from the study interventions. These analyses will be considered exploratory and hypothesis-generating. If y is the endpoint, x1 is the flow rate (1 for high and 0 for low), and x2 is oxygen (1 for oxygen and 0 for ambient air), we will fit the following linear model: y = a + b1*x1 + b2*x2 + b3*x1*x2, with some additional terms. The effect of the flow rate (i.e., the adjusted mean difference between high and low flow) can be calculated as b1 for ambient air and b1 + b3 for oxygen. Similarly, the effect of oxvgen can be calculated as b2 for low flow and b2 + b3 for high flow. Approximate 95% confidence intervals for these effect estimates can be computed given the estimated covariance matrix of the model parameters.

We will estimate the proportion of patients who complete the study; this analysis will include an appropriate 95% confidence interval.

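### The primary model adjusts only for a resting Borg score taken 1 to 5 days before the randomised session and gives no role to the resting score scheduled just before it; the cost is precision, not bias

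*Combined protocol and SAP*

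**What the plan says.** D.2 defines the primary analysis as a general linear model "with a Borg dyspnea score at isotime as the outcome variable". Its listed terms are "flow rate, oxygen, flow rate-oxygen interaction, work rate, and baseline dyspnea at rest, prior to the first exercise test". The only dyspnea score among these terms is "baseline dyspnea at rest, prior to the first exercise test". The longitudinal mixed model is to be fitted "using the same 5 model parameters". The displayed model formula leaves room for further terms but does not name them.

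The timing comes from C.1 and C.7. On day 1, "Patients will first complete an incremental exercise test to familiarize themselves with the cycle ergometer", and C.7 puts a Borg score among the questionnaires given before exercise ("dyspnea survey, cancer dyspnea scale, and dyspnea modified Borg scale"). After a rest, patients do the constant-work-rate test on LFAir. They then "return 3±2 days later to be randomly assigned" to one of the four interventions. At that visit, "The study assessments conducted on the first day will be repeated", and Table 2 marks the Borg scale before as well as during the second structured test.

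C.4 stratifies randomisation by resting Borg score (0-3 versus 4-7) and by work rate. C.6 says that the therapist sets up the device before the patient enters and that flow rate cannot be blinded.

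**The concern.** The randomised comparison takes place entirely in the second session. A patient's breathlessness at rest on that day may differ from day 1, and the day-1 score cannot carry that change. With about 10 evaluable patients per arm, the arms may differ by chance in how breathless patients are when they sit down for the second test. Stratification on a two-level day-1 split does not control this, and the day-1 covariate removes only the part that it predicts. The rest stays in the residual and widens the confidence interval.

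The trial exists to estimate effect sizes (A.1, D.1), so the width of those intervals is its main product. The later reading is already scheduled, yet D.2 does not say whether it is a covariate, the time-zero point of the longitudinal outcome, or unused.

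**Working it through.** **1. The plan's own figure.** Inputs from D.1: 10 per arm, 40 evaluable, 50 enrolled with 20% attrition (40/0.8 = 50), alpha 5%, effects of 1 SD (main) and 2 SD (interaction).

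- Main effect: SE = SD × √(1/20 + 1/20) = 0.316 SD; noncentrality 1/0.316 = 3.162.
- Interaction: SE = SD × √(4/10) = 0.632 SD; noncentrality 2/0.632 = 3.162.
- Two-sided noncentral t power: 86.9% (38 df), 86.8% (36 df), 86.7% (34 df, allowing for the two covariates).

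The stated 86% reproduces. It is in SD units and takes no credit for covariates, so the choice of covariate makes no stated figure wrong.

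**2. Age of the covariate.** 3 − 2 = 1 day to 3 + 2 = 5 days.

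**3. Gain from adding the later score.** Let r1 and r2 be the correlations of the day-1 and session-2 resting scores with the isotime Borg score, and r12 the correlation between the two scores. The documents give none of these. Assumed: r1 = 0.3 or 0.4, r2 = 0.3 to 0.6, r12 = 0.7. Work rate is taken as unrelated to these scores.

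- Variance explained by both: R² = (r1² + r2² − 2·r1·r2·r12)/(1 − r12²), with 1 − 0.7² = 0.51.
- Ratio of standard errors, both scores versus day 1 alone: √[(1 − R²)/(1 − r1²)].

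Worked example, r1 = 0.4 and r2 = 0.6: R² = (0.16 + 0.36 − 0.336)/0.51 = 0.361; ratio = √(0.639/0.84) = 0.872.

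| r1 | r2 | R² | SE ratio | SE narrower by |
|---|---|---|---|---|
| 0.3 | 0.3 | 0.106 | 0.991 | 0.9% |
| 0.3 | 0.4 | 0.161 | 0.960 | 4.0% |
| 0.3 | 0.5 | 0.255 | 0.905 | 9.5% |
| 0.3 | 0.6 | 0.388 | 0.820 | 18.0% |
| 0.4 | 0.3 | 0.161 | 0.9995 | 0.05% |
| 0.4 | 0.4 | 0.188 | 0.983 | 1.7% |
| 0.4 | 0.5 | 0.255 | 0.942 | 5.8% |
| 0.4 | 0.6 | 0.361 | 0.872 | 12.8% |

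Where the later score predicts at most 0.2 better than the earlier one, the range is about 0 to 13%. The pair 0.3/0.6, a difference of 0.3, gives 18%.

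**4. In power terms** (1-SD main effect; 34 df with the day-1 score, 33 df with both): 89.6% to 91.8% at 0.3/0.4, 89.6% to 94.5% at 0.3/0.5, 91.8% to 97.0% at 0.4/0.6.

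**5. Cost of the extra term.** The t quantile moves from 2.032 (34 df) to 2.035 (33 df), about 0.1%. Chance imbalance in a further covariate inflates the variance by about 33/32 on average, so the standard error by √1.031 − 1, about 1.5%. At the bottom of the table (0.4/0.3) the net effect is therefore a loss of between 1% and 2%.

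**The case against.** The strongest reply is that nothing here is an error. The day-1 score precedes randomisation and appears to be the stratifier, so adjusting for it matches the design. Chance differences on the day are ordinary random error, already reflected in the confidence interval. All of that stands.

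A reader might infer that an out-of-date baseline biases the treatment effect, or that any imbalance on the day passes in full into the estimate. The documents support neither: the comparison is randomised, and the day-1 score absorbs what it predicts. A reader might also cite the background statement on breakthrough episodes as evidence that resting dyspnea drifts between visits. That statement is mainly about exertion, so the superiority of the later score remains an assumption. Nor does Table 2, which does not mark a Borg score in its warm-up column, show that the day-1 score goes uncollected; C.7 lists it.

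The most serious objection concerns timing. The device is set up before the patient enters, flow is unblinded, and the documents do not say whether the session-2 resting score comes before the patient meets it. If it comes after, it is a post-exposure variable, and adjusting for it could bias the flow effect. The objection is sound against an untimed reading; a stated timing rule answers it.

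**Conclusion.** The point holds as a question of precision. D.2 leaves out a same-day resting score that the trial already plans to take, and the planned covariate is 1 to 5 days old. No bias follows and no stated figure is wrong.

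Under the assumed correlations the standard error narrows by about 0 to 13% (18% at the most favourable pair), less about 1.5% for the extra term. The net benefit could be nil or slightly negative if the later score predicts no better than the earlier one. It would also be smaller if the LFAir isotime Borg score, a separate covariate, were in the model. The percentages in the table do not depend on the number of patients; the cost of the extra term does. The change is worth making because it is cheap and because the role of the reading should be fixed before the data are seen.

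**What to change.** In D.2:

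- Keep the day-1 resting Borg score, as the stratifier, in the model.
- Add the session-2 resting Borg score as a prespecified covariate in the primary model.
- In the longitudinal model, enter it as a covariate and not as an outcome point, and revise the count of model parameters to match.
- State that it must be recorded before the cannula and gas are applied and before the patient can see or feel the flow rate. Readings not taken under that rule are post-exposure and should not be used for adjustment.

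The cost is SAP wording, one degree of freedom, and a fixed time point for a reading that is already scheduled. No visit or procedure is added. If readings have already been taken without a documented time relative to set-up, they cannot be assumed usable for this purpose.
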